**Office Title: Transcutaneous Auricular Vagus Nerve
Stimulation for Preventing Acute Kidney Injury in Patients
Undergoing Cardiac Surgery With Cardiopulmonary
Bypass: A Randomized Controlled Trial
NCT number: Not yet assigned
Protocol Number: 20260315122240876
Version: V1.0
Version date: February 6, 2026**

Transcutaneous Auricular Vagus Nerve Stimulation for Preventing Acute Kidney Injury in Patients Undergoing Cardiac Surgery With Cardiopulmonary Bypass: A Randomized Controlled Trial

Research Protocol

I. Research Background

Acute kidney injury (AKI) is one of the most common and severe complications following cardiac surgery, characterized by a rapid decline in renal function within hours to days [1-3]. Despite continuous advancements in cardiac surgical techniques, the incidence of postoperative AKI remains as high as 10.4% – 42%, with approximately 2% – 3% of patients requiring renal replacement therapy [2-7]. AKI not only significantly prolongs patients' time in the intensive care unit (ICU) and overall hospital stay but is also strongly associated with increased 30-day and long-term mortality rates, posing a major threat to patient prognosis [2,4]. Cardiopulmonary bypass (CPB), as a critical technical support for cardiac surgery, can induce ischemia-reperfusion injury, systemic inflammatory responses, and autonomic dysfunction due to non-physiological perfusion [8-11], leading to a further increase in the incidence of CPB-associated AKI to 20.8% – 50.8%. The risk is significantly positively correlated with CPB duration and is particularly prominent in complex surgeries [2-6,12-18].

Regarding the prevention of CPB-associated AKI, current clinical strategies primarily focus on perioperative hemodynamic optimization, volume management, and pharmacological interventions. However, these measures are predominantly supportive in nature and fail to fundamentally prevent the onset and progression of AKI [9,19,20]. Although previous studies have explored various pharmacological and blood purification interventions, there remains a lack of highly evidence-based specific therapies with robust high-level evidence [21-23]. This situation

highlights the fundamental limitations of current prevention strategies centered on systemic hemodynamic support and nonspecific anti-inflammatory measures, underscoring the urgent need for novel intervention strategies targeting new mechanisms and targets to overcome the challenges in AKI prevention.

Recent studies have demonstrated that excessive activation of the sympathetic nervous system and inhibition of the parasympathetic nervous system are key driving factors in the occurrence and progression of CPB-associated AKI, with inflammatory responses playing a central role [24-27]. Renal ischemia-reperfusion induced by extracorporeal circulation significantly enhances sympathetic nerve activity, disrupts renal vascular homeostasis by releasing catecholamines and activating the renin-angiotensin system, leading to vasoconstriction, inadequate perfusion, and inflammatory cell infiltration, thereby exacerbating tubular injury and creating a vicious cycle [25,26,28-31]. In this context, vagus nerve stimulation represents an emerging strategy that modulates immune and autonomic functions through electrical stimulation of the vagus nerve [25,32,33], which can mitigate inflammatory responses and improve circulatory function by restoring sympathetic-parasympathetic balance and activating the cholinergic anti-inflammatory pathway (CAP) [26,33-35].

Recent studies have revealed that after vagus nerve activation, signals are transmitted to CD4⁺ T cells in the spleen via the splenic nerve, promoting their release of acetylcholine. This subsequently activates macrophages expressing $\alpha 7$ nicotinic acetylcholine receptors ($\alpha 7$ nAChR), inhibiting the release of pro-inflammatory factors and alleviating systemic and renal local inflammation [24,26,33,36,37]. Transcutaneous auricular vagus nerve stimulation (ta-VNS), as a non-invasive technique, can induce physiological effects similar to invasive stimulation by stimulating the auricular branch of the vagus nerve in the auricular region. It activates CAP and demonstrates organ-protective effects. Preclinical studies have confirmed its ability to improve renal function, reduce levels of renal injury markers, and inhibit the release of inflammatory factors and oxidative stress responses in CPB models [25,32,34,35,37-41].

Although ta-VNS has demonstrated potential value in preventing CPB-associated AKI, there remains a lack of rigorously designed randomized controlled trials providing high-level clinical evidence. To address this research gap, this study aims to systematically evaluate the efficacy and safety of ta-VNS in preventing AKI during cardiopulmonary bypass in cardiac surgery patients

through a meticulously designed randomized controlled clinical trial. The goal is to develop an innovative neuromodulation strategy for perioperative renal protection.

II. Research Objective

This study aims to evaluate the efficacy of perioperative transcutaneous auricular vagus nerve stimulation (ta-VNS) in reducing the incidence of postoperative acute kidney injury (AKI) in patients undergoing elective cardiopulmonary bypass surgery through a randomized controlled trial. The hypothesis posits that perioperative ta-VNS application significantly lowers the AKI incidence rate within 7 days postoperatively compared to sham stimulation. Additionally, this study will investigate the effects of ta-VNS on AKI severity, related renal function parameters, and biomarkers to validate its clinical value as a non-invasive neuromodulation approach for perioperative renal protection.

III. Research Design and Methods

3.1 Study Design

This study is a randomized controlled, intervention-based clinical trial. Eligible patients were randomly assigned in a 1:1 ratio to either the ta-VNS group or the sham stimulation group. The primary endpoint was the incidence of acute kidney injury (AKI) within 7 days postoperatively. The objective of this study was to evaluate the efficacy and safety of continuous 6-day perioperative ta-VNS intervention in reducing the incidence of AKI following cardiac surgery under cardiopulmonary bypass (CPB).

3.2 Study Subjects

3.2.1 Inclusion Criteria

- 1) Age ≥ 18 years.
- 2) Scheduled elective CPB cardiac surgery to be performed under general anesthesia.
- 3) Baseline serum creatinine level for calculating eGFR ≥ 60 mL/min/1.73 m².
- 4) Classified as Grade I-III by the American Society of Anesthesiologists (ASA).
- 5) Cardiac function classification as Class I-III according to the New York Heart Association (NYHA) criteria.
- 6) Possess adequate comprehension and communication skills to collaborate with the

research process.

7) Voluntary participation in this study and signing of the informed consent form. If the subject is unable to read and sign the informed consent form due to lack of capacity for behavior or other reasons, their guardian must act as proxy for the informed consent process and sign the form. If the subject lacks the ability to read the informed consent form (e.g., illiterate subjects), a witness must observe the informed consent process and sign the form.

3.2.2 Exclusion Criteria

1) Unilateral kidney or post-renal transplantation (RRT) with preoperative AKI (KDIGO criteria) or preoperative RRT.

2) Contraindications for ta-VNS implantation include active infections, dermatitis, skin lesions, or severe psoriasis in the bilateral auricular stimulation areas; hypersensitivity to stimulator materials such as silicone or electrode gel; concurrent uncontrolled arrhythmias, symptomatic bradycardia, sick sinus syndrome, second-degree or higher atrioventricular block; existing cardiac pacemakers or defibrillators; carotid sinus hypersensitivity; uncontrolled epilepsy; or active peptic ulcers.

3) Received vagus nerve stimulation, auricular acupuncture, or transcutaneous electrical nerve stimulation treatment within 1 month prior to enrollment.

4) Drugs used long-term and unable to be safely discontinued preoperatively, which significantly affect autonomic nerve tone or renal blood flow.

5) Preoperative presence of active systemic infection or sepsis (based on Sepsis-3 criteria).

6) History of acute ischemic or hemorrhagic stroke or acute myocardial infarction within 3 months prior to enrollment.

7) Concurrent severe hepatic insufficiency (Child-Pugh class C), acute liver failure, or other serious comorbidities.

8) Vulnerable populations excluding the elderly/illiterates, including critically ill patients, psychiatric disorders, individuals with cognitive impairment, and pregnant women.

9) Other circumstances where the investigator deems the subject unsuitable for participation in the study.

3.2.3 Exit Criteria

1) The subject or their legal representative requests to withdraw from the study.

- 2) Development of intolerable ta-VNS-related adverse reactions (e.g., severe skin hypersensitivity, pain, dizziness, etc.).
- 3) Perioperative changes in condition (e.g., prolonged sedation, reoperation) render continued stimulation unfeasible.
- 4) The investigator determined that the subject was not suitable to continue participating in the study.

3.3 Research Content

3.3.1 Stratification, Blinding, and Intervention

After stratifying subjects according to the Cleveland Clinic scoring system for predicted dialysis-required AKI risk (high risk: ≥ 6 points vs. low-to-moderate risk: 1-5 points), independent statisticians generated computer-generated block random sequences (block size: 2 or 4) to assign participants at a 1:1 ratio to either the ta-VNS group or sham stimulation group. The grouping results were sealed in sequentially numbered opaque envelopes.

Blinding was implemented for both participants and outcome evaluators. After obtaining informed consent from participants, a non-blind study coordinator who would not be involved in subsequent clinical work publicly opened the envelope, recorded the grouping information, and handed it to a trained non-blind operator to execute the corresponding stimulation protocol. Other researchers (including those responsible for follow-up, data collection, testing, and statistical analysis) remained unaware of the grouping assignments.

The ta-VNS group received electrical stimulation via a transcutaneous auricular vagus nerve stimulator (tVNS501) applied to the left auricular cartilage. The parameters were set as follows: frequency 25Hz, pulse width 250 μ s, with a stimulation-interval cycle of 30 seconds stimulation followed by 30 seconds rest. The stimulation intensity was incrementally increased starting from 0.4V in 0.4V increments until the subject experienced pain, then adjusted downward to just below the pain threshold to determine the optimal stimulation intensity. The stimulation coverage spanned preoperative, intraoperative, and postoperative phases: beginning on the day of surgery upon entering the preoperative preparation room and continuing until the patient was transferred to the ICU, followed by 6 hours of stimulation. From postoperative days 1 to 5, the stimulation regimen was restored to twice daily (at 9:00 AM and 2:00 PM) with each session lasting 120 minutes [42-44].

In the sham-stimulation group, electrodes were placed at the same site and within the same cycle period with optimal intensity determined, but stimulation output was turned off without administering actual electrical stimulation.

All equipment was dedicated to specific individuals and labeled for identification. Participants were informed that the stimulation process might induce or fail to induce any discomfort. Heart rate and blood pressure were continuously monitored during the intervention. If persistent heart rate <50 beats per minute, significant hemodynamic instability, or other severe adverse events occurred, stimulation was immediately discontinued and recorded.

The tympanic vagus nerve stimulator (tVNS501) involved in this study exhibits off-label use (off-label indication). The tympanic vagus nerve stimulator (tVNS501) (as specified in the package insert) may be used as adjunctive therapy for sleep disorders, fatigue, anorexia, and anxiety symptoms; when combined with medications, it is applicable for adjunctive treatment of diabetes mellitus. In this study, the tympanic vagus nerve stimulator (tVNS501) was employed to prevent AKI following cardiac surgery under CPB, constituting off-label use. Only the left ear unit was utilized in this study, as the device's built-in metal electrodes enable precise stimulation of the cochlear cone. Although the right ear unit was available, it lacked stimulation functionality and was neither worn nor activated during the study.

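### Opening the envelope publicly contradicts the stated blinding, and printed block sizes of 2 or 4 weaken concealment for later patients

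*Combined protocol and SAP*

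**What the plan says.** All the allocation text is in section 3.3.1 (Stratification, Blinding, and Intervention).

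- **Sequence.** Patients are stratified into two groups by Cleveland Clinic score. Independent statisticians prepare "computer-generated block random sequences (block size: 2 or 4") "to assign participants at a 1:1 ratio". The rule for mixing the two sizes is not given.
- **Envelopes.** They are sealed, opaque and numbered in order.
- **Opening.** "After obtaining informed consent from participants", the envelope is opened by "a non-blind study coordinator who would not be involved in subsequent clinical work". That person "publicly opened the envelope, recorded the grouping information, and handed it to a trained non-blind operator to execute the corresponding stimulation protocol".
- **Blinding.** Participants and outcome evaluators are said to be blinded. The remaining researchers, with follow-up, data collection, testing and analysis named, "remained unaware of the grouping assignments". Section 3.3.2.1 adds that the clinicians who diagnose AKI are blinded.

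The protocol does not say where the envelope is opened, who may watch, whether the patient is there, or whether the coordinator or operator has any part in screening, consent or scheduling.

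**The concern.** There are two linked problems.

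The first is a contradiction within one paragraph. An opening that is public in any ordinary sense shows the group to someone other than the coordinator. A site that followed the instruction literally could reveal the group to the patient, a data collector or an assessor, all of whom the same section describes as unaware.

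The second concerns the next patient. Opening after consent protects the allocation of the patient who has just consented. It does not protect the following one if people involved in enrolment know the history and the block sizes, and the sizes are in the protocol itself. Section 3.2.2 leaves room for judgement (serious comorbidities in general, and unsuitability in the investigator's opinion), so a foreseen allocation could influence who is enrolled and when.

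At stake are selective enrolment and differences in care. One AKI criterion is urine output, which care can influence, and several secondary outcomes (pain, sleep, QoR-15) are reported by patients. Blinded AKI diagnosis protects the classification of outcomes. It does not protect against selection or altered care, and no analysis in section 3.3.3 would correct for either.

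**Working it through.** **Text check.** Set side by side, "publicly opened the envelope, recorded the grouping information" and "remained unaware of the grouping assignments" are compatible only if nobody but the coordinator and operator is present. The first statement says the opposite, and nothing else in the protocol limits attendance.

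**Predictability.** The plan gives no figure to reproduce. Inputs from section 3.3.1 are 1:1 allocation, blocks of 2 or 4, and separate lists in two strata. My assumptions are that the two sizes are equally likely and that the observer knows all past allocations in the stratum and the possible sizes, but is not told where blocks begin.

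For a block of size 2n:
- Expected number of allocations made when the arms are level: E(n) = 4^n / C(2n, n) − 1.
- Allocations that go to the lagging arm: always n, because each step away from balance is matched by one step back.
- Expected correct guesses, choosing the lagging arm when there is one and tossing a coin otherwise: n + E(n)/2.

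Block of 2: E(1) = 4/2 − 1 = 1, so correct = 1 + 0.5 = 1.5.
Block of 4: E(2) = 16/6 − 1 = 1.667, so correct = 2 + 0.833 = 2.833.

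One block of each size makes 6 allocations:
- Correct guesses: (1.5 + 2.833)/6 = 4.333/6 = **72%**.
- Arms unequal: (6 − 1 − 1.667)/6 = 3.333/6 = **56%**.
- Next is the lagging arm, given unequal arms: (1 + 2)/3.333 = **90%**.
- Certain allocations: one third of 4-blocks start with two patients in the same arm (2 of 6 orderings). That start rules out a block of 2, so the third and fourth allocations are both forced. This gives (1/3 × 2)/6 = 1/9 = **11%**.

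A simulation with Bayesian updating over unknown block boundaries gives 72% correct and 11% certain, whether 76 or 152 allocations are run.

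**If the mix is different.** All blocks of 2: 1.5/2 = 75% correct and 50% certain. All blocks of 4: 2.833/4 = 71% correct and (1/3 + 1)/4 = 33% certain. Correct guesses therefore stay between 71% and 75%. The share known with certainty depends heavily on the unstated mixing rule.

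**Illustrative alternative: 4, 6 and 8, equally likely.** E(3) = 64/20 − 1 = 2.2 and E(4) = 256/70 − 1 = 2.657. The sum of E over the three sizes is 1.667 + 2.2 + 2.657 = 6.524, in 18 allocations.
- Correct: (9 + 6.524/2)/18 = 68%.
- Arms unequal: (18 − 6.524)/18 = 64%.
- Lagging arm, given unequal arms: 9/11.476 = 78%.
- Certain: about 2% (2.2% by the same simulation).

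| Scheme | Correct guesses | Lagging arm when unequal | Certain |
|---|---|---|---|
| 2 and 4 | 72% | 90% | 11% |
| 4, 6 and 8 | 68% | 78% | 2% |

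**The case against.** A reader might infer that staff at the opening learn every allocation and can predict the next, so that concealment and blinding are defeated. The documents do not support this.

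- They do not say who is present. The word may be loose phrasing, and handing the group to a single operator would have little purpose if everyone had watched.
- The sequence comes from independent statisticians. The envelopes are sealed, opaque, numbered and opened only after that patient's consent, the opener has no later clinical role, and blinded clinicians diagnose AKI. Any predictability affects later patients only.
- Prediction needs the full history within a stratum, and no section says that the coordinator or operator enrols patients. Even with that history, most allocations are guessed rather than known.
- Larger blocks gain little in overall guessing (72% to 68%), and the arms are unequal more often (64% against 56%). Stratum sizes are not given, and if the high-risk stratum is small, small blocks are a defensible way to keep balance.

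These points limit the strength of the finding but do not remove it. The instruction as written still conflicts with the blinding statement. The coordinator is barred from later clinical work, but neither that person nor the operator is barred from enrolment. The sizes are in a document that site staff hold. The case for changing the blocks is weaker than the case for changing the text, and rests mainly on the drop in certain allocations, about fivefold.

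**Conclusion.** The point stands in two limited parts. First, section 3.3.1 contradicts itself on who learns the group, and this needs correcting whether or not anyone has in fact been unblinded. Second, for anyone who knows the past allocations in a stratum, the printed block sizes allow about 72% correct guesses against 50% by chance, about 90% predictability when the arms are unequal, and certainty for about 11% of allocations. These figures assume equally likely sizes. With a single size throughout, correct guesses would be 71% to 75% and certain allocations 33% to 50%.

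This weakens concealment for later patients. It does not show that concealment has failed or that the primary comparison is biased, because the documents do not establish that anyone with this knowledge enrols, treats or assesses patients. The planned total of 152 does not depend on this point.

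**What to change.** In section 3.3.1:

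1. Delete the word publicly. State that the coordinator opens the envelope alone, out of sight of the participant and of enrolling, treating and assessing staff, and tells only the operator.
2. State that neither the coordinator nor the operator screens, consents or schedules patients.
3. Drop block size 2 and use larger, randomly varied blocks within each stratum. Replace the printed sizes with a statement that they are held in a separate document by the independent statistician. Sizes 4, 6 and 8 are used above for illustration only; whatever is chosen should not appear in the site protocol.

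No new rule on timing is needed, because section 3.3.2.3 already requires baseline measurements to be complete before randomization.

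The cost is a few sentences and one new list, with no change in sample size. The downside is balance. With blocks of 8, a stratum that ends mid-block can be out by up to 4 patients, against up to 2 with blocks of 4. With two strata the worst case overall is 2 × 4 = 8 of 152. If the high-risk stratum is expected to be small, the statistician can weigh this when choosing its sizes.

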the Confusion Assessment Measure (CAM) or the ICU Confusion Assessment Measure (CAM-ICU) for both preoperative and postoperative periods (over 7 consecutive days). Early cognitive function was screened using the Mini-Mental State Examination (MMSE) on preoperative day 1, postoperative day 3, and postoperative day 7. Sleep quality was evaluated using the Richards-Campbell Sleep Questionnaire (RCSQ) on preoperative day 1, postoperative day 1 morning, and postoperative day 3 morning to assess prior night sleep status. Recovery quality was scored using the 15-item Quality of Recovery Scale (QoR-15) on preoperative day 1, postoperative day 1, postoperative day 3, and postoperative day 7. Pain and analgesic demand were recorded as baseline pain levels on preoperative day 1 and pain numerical scores (NRS) within 48 hours postoperatively (recorded at least once daily), along with total opioid consumption within 48 hours postoperatively (converted to oral morphine equivalents).

7) Perioperative complications and mortality rate

The incidence rates of cardiovascular complications (including new-onset atrial fibrillation and other arrhythmias, acute myocardial infarction, postoperative myocardial injury, and low cardiac output syndrome), stroke, pulmonary embolism, pulmonary infection, deep vein thrombosis, surgical site deep infection, and all-cause mortality within 30 days postoperatively.

8) Resource consumption

Length of hospital stay, ICU stay duration, and re-admission rate due to complications.

9) Biomarkers

To comprehensively evaluate patient status and explore the pathogenesis of AKI, this study detected the following biomarkers:

a) Routine testing: Collect daily routine laboratory data before surgery and for 7 days postoperatively, including C-reactive protein (CRP), neutrophil-to-lymphocyte ratio (NLR), cardiac troponin (cTn), creatine kinase isoenzyme MB (CK-MB), N-terminal pro-brain natriuretic peptide (NT-proBNP), and serum cystatin C.

b) Specific inflammatory markers and renal injury indicators: Peripheral blood samples were collected at 24h, 48h, and 72h postoperatively and placed in EDTA anticoagulation tubes. Plasma interleukin-6 (IL-6) and neutrophil gelatinase-associated lipocalin (NGAL) concentrations were detected in batches using the ELISA method.

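### Sham patients have their intensity set by titration to pain and then get no output, so they are likely to be able to tell their arm; the stated participant blinding is neither secured nor checked, and the patient-reported secondary outcomes are exposed

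*Combined protocol and SAP*

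**What the plan says.** All of the following is in section 3.3.1 unless stated otherwise.

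- The claim: "Blinding was implemented for both participants and outcome evaluators".
- The working intensity is found by stepping the output up from 0.4V in 0.4V increments "until the subject experienced pain, then adjusted downward to just below the pain threshold to determine the optimal stimulation intensity".
- In the sham arm the electrodes go on the same site "within the same cycle period with optimal intensity determined, but stimulation output was turned off".
- Stimulation begins in the preoperative preparation room, runs through surgery and for 6 hours in the ICU. On postoperative days 1 to 5 it is then given "twice daily (at 9:00 AM and 2:00 PM) with each session lasting 120 minutes".
- The one measure aimed at what participants expect is this: "Participants were informed that the stimulation process might induce or fail to induce any discomfort".

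Section 3.3.2.2, item 6, lists the outcomes that depend on the patient. For QoR-15 it says "Recovery quality was scored using the 15-item Quality of Recovery Scale (QoR-15) on preoperative day 1, postoperative day 1", and then again on postoperative days 3 and 7. RCSQ is completed preoperatively and on the mornings of days 1 and 3. Pain NRS and opioid consumption cover the first 48 hours.

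Section 3.3.3 compares NRS and opioid use by t-test or Mann-Whitney test, and analyses QoR-15 and RCSQ by GEE with a group-by-time interaction. Neither section mentions an arm guess, a blinding index or any analysis that allows for unblinding.

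**The concern.** A silent sham can work when the patient does not know what the live device feels like. Here the plan's own wording removes that condition. Read plainly, every patient is taken up to pain once, so every patient holds a reference sensation. One arm then goes on feeling something close to it in 30-second bursts, and the other feels nothing.

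At stake is the reading of the self-reported recovery outcomes. If patients can tell their arm, a difference in QoR-15, sleep, pain or opioid demand cannot be separated from what they expected of the device. The expectation is not remote from the endpoints: section 3.3.1 records that the stimulator is labelled as adjunctive therapy for sleep disorders, fatigue and anxiety symptoms, among other uses.

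**Working it through.** **1. What each arm would feel.**

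| Stage | Active | Sham |
|---|---|---|
| Setting the intensity | Raised to pain, then lowered | Intensity also determined, by the same definition |
| Preoperative room | Output slightly under the pain level, 30 s on, 30 s off | No output |
| Days 1 to 5 | As above | No output |

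The discomfort statement prepares patients for the possibility of no discomfort. It does not tell them that a working device may produce no sensation at all, and it cannot undo what a sham patient felt during titration.

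**2. Exposure before each assessment.** Postoperative sessions: 5 days × 2 = 10, and 10 × 120 min = 20 h. With a 30 s/30 s cycle, half of that, 10 h, is live output in the active arm. Sessions are at 9:00 and 14:00, so:

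- RCSQ on the morning of day 1 may precede any postoperative session.
- RCSQ on the morning of day 3 follows about 2 days × 2 = 4 sessions (8 h).
- NRS and opioid use over 48 h overlap about 4 sessions.
- QoR-15 on day 1 can follow at most 2 sessions. On day 3 it follows at least 4, and on day 7 it follows all 10 (20 h).

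**3. Number of patients.** Section IV gives 17.1% against 37.9%, two-sided 0.05 and power 0.80. With unpooled variance, n = (1.960 + 0.842)² × (0.171 × 0.829 + 0.379 × 0.621) / 0.208² = 68.4 per arm, against the stated 68. Allowing for dropout, 68 / 0.90 = 75.6, so 76 per arm and 152 in all, as stated. (A pooled-variance formula gives 72; nothing here depends on the choice.) I use 68 as the evaluable number and 76 as the upper limit.

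**4. Illustration of what a reporting shift could do.** The documents give no SD and no estimate of bias for these scales, so the shift d, in SD units, is an assumption. With no true effect, SE = √(2/n), and P(two-sided P<0.05) ≈ Φ(d/SE − 1.96), ignoring the far tail.

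| d | n = 68, SE = 0.171 | n = 76, SE = 0.162 |
|---|---|---|
| 0.2 | 21% | 23% |
| 0.3 | 42% | 46% |
| 0.5 | 83% | 87% |

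For example, with n = 76 and d = 0.3, 0.3/0.162 = 1.85, and Φ(1.85 − 1.96) is about 46%. The nominal rate is 5%. The formula describes one comparison of two means. It is closest to the planned tests for NRS and opioid use, and it does not describe the GEE interaction tests for QoR-15 and RCSQ.

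**The case against.** The strongest reply is that nothing in the documents shows that blinding fails. They contain no arm guesses and no sensory reports, and some stimulation falls under anaesthesia or sedation; section 3.2.3 foresees prolonged sedation in some patients. That stands. A reader might infer that participant blinding is known to be broken, but the text supports only that it is likely to be compromised and is untested.

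Three other strong inferences also fail:

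- **That bias must favour the active arm.** Expectation could push that way, but section VII lists pain and local skin discomfort among the main adverse events, so felt stimulation could worsen pain or comfort scores. The direction is unknown.
- **That patients complete the questionnaires during 20 h of stimulation.** No section places assessments within sessions, and only the day-7 QoR-15 follows the whole course.
- **That the trial's main result is in doubt.** AKI is diagnosed on creatinine and urine output by clinicians unaware of allocation, and follow-up, data collection and testing staff are also kept unaware. Recovery quality is not named in the section II objectives, and no section plans a claim of benefit on it.

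It could also be said that sham patients are not really titrated. The text says that their intensity is determined. If it were not, sham patients would lack the reference sensation and the inference about them would weaken. The arms would still differ, because only active patients would have been taken to pain and then felt the device at each waking session.

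**Conclusion.** The concern holds as a gap between a stated property and the design. Section 3.3.1 claims participant blinding, describes a sham sequence that is likely to let patients recognise their arm, offers one statement that mitigates this only in part, and provides no check.

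The outcomes exposed are QoR-15 on days 1, 3 and 7, the day-3 RCSQ, 48-hour pain NRS and opioid use. The size and direction of any bias are unknown. The 21%, 42% and 83% figures (23%, 46% and 87% at 76 per arm) show how sensitive a simple comparison would be to assumed shifts of 0.2, 0.3 and 0.5 SD; they are not error rates of the planned analysis. The conclusion rests on reading the sham description as written and on patients being awake enough to notice output in the preoperative room or in most sessions from day 1. The creatinine-based primary endpoint is largely protected, so this limits what the secondary outcomes can show and does not threaten the main comparison.

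**What to change.** 1. Reconcile the description of the sham sequence with the blinding claim in section 3.3.1. Restate the claim as: outcome assessors and laboratory blinded; participant blinding attempted but not assured.
2. Ask each participant once which arm they believe they are in, and why. Do this early, for example after the first awake postoperative session, before any perceived benefit could drive the answer. Ask the QoR-15/CAM/MMSE assessor the same at an existing contact. Report the guesses, or a blinding index, by arm and descriptively.
3. Prespecify in section 3.3.3 that QoR-15, RCSQ, pain NRS and opioid use are interpreted as open to reporting bias and do not on their own support a claim of benefit, whatever the guesses show. A rule that reclassifies these outcomes when guesses exceed chance is not advisable: patients who truly recover better may guess active for that reason, and the rule would then penalise a real effect.

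The cost is one extra question for the participant and one for the assessor, a few sentences in the protocol and analysis plan, and weaker claims on these secondary outcomes. The guesses need to be planned now, because they cannot be collected reliably afterwards.
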